3.3 Interventions

3.3.1 Control arm:

Active Comparator: Change the dressing 24 hours after CVC catheterization (CD24h treatment)

Patients in this arm will receive standard dressing change operations. The dressing change will be performed 24 hours after CVC catheterization in the operating room or PICU, and then the second dressing change will be completed seven days later (if there are no clinical indications such as fluid oozing and bleeding). Skin flora sampling will be performed on the eighth day after CVC catheterization. The sampling method is detailed in the protocol.

3.3.2 Experimental arm:

Intervention: Change the dressing seven days after the CVC catheterization (CD7d treatment)

Patients in this arm will change the dressing seven days after the CVC catheterization in the operating room or PICU (if there are no clinical indications such as fluid accumulation and bleeding). Skin flora sampling will be performed on the seventh day after CVC catheterization when the dressing is changed. The sampling method is exactly the same as that of the control group.

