3.5 Blinding

The sample collectors and laboratory personnel will be blinded to the assignment of the patients. The trial statistician will also be blinded regarding the treatment code when developing the statistical analysis plan and writing the statistical programs. The actual allocation will only be provided to the study team after the database lock.

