4.1 Study population data sets

Two study populations will be considered in the analysis as follows:

- **Intent-to-Treat population**

Intent-to-treat (ITT) population will be defined at the moment the randomization is performed. For example, if a participant receives the wrong treatment or no treatment at all or is lost for follow-up for outcomes, he/she will be analyzed according to the arm to which they were allocated. This will be the primary analysis for the trial. Participants will be excluded from the ITT analysis if the primary outcome is missing, forming a modified ITT population (mITT).

- **Per-protocol population**

Per-protocol (PP) population will only include patients who received the treatments according to the protocol. In addition, the patients in the CD7d group completed skin sample collection on the seventh day after CVC catheterization, and the patients in the CD24h group completed it on the eighth day.

Participants will be excluded from the PP population if they:

- Did not adhere to per-protocol treatment, including the CD7d group changing the dressing less than seven days after CVC catheterization, or the CD24h group does not change the dressing more than 24 hours after CVC catheterization.
- Switched treatment.

This population will be used for the supportive analyses.

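### Does the per-protocol definition in SAP section 4.1 need one identical rule for clinically indicated dressing changes in both arms?

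*SAP*

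**What the plan says.** Section 3.3 of the SAP makes the scheduled change conditional in each arm. For the second CD24h change the condition is "if there are no clinical indications such as fluid oozing and bleeding"; for the day-7 CD7d change it is "if there are no clinical indications such as fluid accumulation and bleeding". Unscheduled, indicated changes are therefore expected in both arms. For CD7d, section 3.3 adds: "Skin flora sampling will be performed on the seventh day after CVC catheterization when the dressing is changed".

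Section 4.1 gives the general PP test: "Per-protocol (PP) population will only include patients who received the treatments according to the protocol". It also requires a skin sample on day 7 (CD7d) or day 8 (CD24h). Its exclusions are non-adherence, introduced as a list of examples containing "the CD7d group changing the dressing less than seven days after CVC catheterization, or the CD24h group does not change the dressing", and "Switched treatment". The CD24h example reads in full: "the CD24h group does not change the dressing more than 24 hours after CVC catheterization". The section gives the PP set a supportive role, and section 5.1.2 lists the PP analysis among the sensitivity analyses.

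**The concern.** Consider two patients, one per arm, who both ooze on day 4, have the dressing changed for that reason, and are sampled on the planned day. Under the named criteria the CD7d patient leaves the PP set. Nothing named removes the CD24h patient, whose 24-hour change was done. The PP comparison would then condition on a post-randomisation event in one arm only, and oozing or bleeding could plausibly be related to colonization.

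In a non-inferiority trial the PP result is read beside the primary result, and PP and adjusted PP fill two of the four rows of Table 2. Differential selection would make agreement or disagreement between those rows harder to interpret. The CD24h criterion is also awkwardly phrased: it could describe a 24-hour change that was omitted, made late or made too early.

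**Working it through.** **The plan's own figure.** Section 3.6 assumes 55% in both arms, a margin of 20 points, one-sided alpha 0.025 and power 80%. Then n = (1.960 + 0.842)² × 2 × 0.55 × 0.45 / 0.20² ≈ 97.1, so 98 per group, and 98 / 0.70 = 140 after drop-out. Both figures reproduce, and neither depends on the PP definition.

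**The criteria beside the design.** Section 2.1 states the comparison as a dressing change after seven days against one after 24 hours, and section 3.3 names the arms accordingly. The section 4.1 examples track that:

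| Arm | Defining first change | Named PP failure |
|---|---|---|
| CD7d | at seven days | changed before seven days |
| CD24h | at 24 hours | 24-hour change not carried out as planned |

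A day-4 change is thus not the same event in the two arms. In CD7d it ends the undisturbed period that is the assigned treatment. In CD24h the defining change has already been made.

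**Who is affected.** A CD7d patient matters here only if changed early and still sampled on day 7. Section 3.3 ties that sample to the day-7 change, so a patient changed early and not sampled on day 7 is already out under the sampling condition.

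**Size, for illustration.** The SAP gives no early-change rate and no link between early change and colonization. Assume 98 otherwise eligible patients per arm, 55% in each, and k CD7d patients whose risk differs by d = ±20 points from the CD7d average.

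- Shift if they leave CD7d only: k / (98 − k) × 20, opposite in sign to d.
- Half-width if k leave both arms: 1.96 × √(2 × 0.55 × 0.45 / (98 − k)).
- A true 20-point CD7d excess if they stay in both arms and show no excess: 20 × (1 − k/98).

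| k | Shift, CD7d only (points) | Half-width, exclude in both (points) | Excess seen, retain in both (points) |
|---|---|---|---|
| 0 | 0 | 13.9 | 20.0 |
| 1 | 0.2 | 14.0 | 19.8 |
| 5 | 1.1 | 14.3 | 19.0 |
| 10 | 2.3 | 14.7 | 18.0 |

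For k = 10 and d = −20 the CD7d rate becomes 57.3% in 88 patients. The upper limit is 2.3 + 196 × √(0.573 × 0.427/88 + 0.2475/98) ≈ 2.3 + 14.3 = 16.6 points, still below 20.

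A wider range measures d against the remaining patients, so the shift is share × d. Shares of 5% to 30% and gaps of 10 to 30 points give 0.5 to 9 points in either direction. At the unfavourable extreme (64% in 69 CD7d patients) the upper limit is about 9 + 15 = 24 points and the PP row would fail. That needs 30% of the on-time-sampled CD7d patients to have been changed early, with a risk 30 points higher than the rest had they shifted the other way or, as here, 30 points lower. Nothing in the SAP supports either figure.

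**The case for a change.** The best case for a change is that section 4.1 itself writes arm-specific PP criteria, so the matter cannot simply be left to the protocol. An open list leaves membership to judgement. Section 3.5 says: "The actual allocation will only be provided to the study team after the database lock". A rule fixed before that point would remove the discretion. The CD24h phrase could also lead two programmers to different PP sets, whether or not the asymmetry is intended.

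Part of this stands. The CD24h wording is loose, and the SAP does not say how an indicated extra change counts in that arm. But set beside section 3.3.1, the natural reading is a 24-hour change that was omitted or late. The general test can also cover a mid-week CD24h change if the protocol treats it as a deviation; reading silence as inclusion is only one interpretation. Discretion is limited as well, because section 3.5 keeps the statistician blinded to the treatment code while the programs are written.

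Whether an indicated CD7d change at about 24 hours is also a switch makes no difference to membership: the named CD7d criterion already excludes it. The section 7 list has no dressing-change or sampling dates, but it is plainly not the full data set, since it also omits the administration set used for adjustment in section 5.1.2.

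**Conclusion.** No change is called for. A PP set may be stricter than permitted care, so excluding a foreseen early change in CD7d does not contradict section 3.3, and such patients with an observed outcome stay in the primary analysis. An identical rule is not clearly better. Retaining early-changed patients in both arms dilutes the contrast, which matters in a non-inferiority trial; excluding them in both costs precision and still selects on a post-randomisation event. Nor would it necessarily remove equal numbers, because the 24-hour change in CD24h can absorb early indications.

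With up to 10 affected patients of 98 and a 20-point gap, the effect is at most 2.3 points against a half-width of 13.9, in supportive rows only. This rests on assumed inputs; a large effect would need far more early changes among patients sampled on day 7. The loose CD24h phrase and the unstated handling of indicated CD24h changes are details that analysts can settle sensibly when they build the PP set. The primary result, the 20-point decision rule and the sample size do not depend on them.

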2.1 Study Objective

The primary objective is to compare the occurrence of skin bacterial colonization in patients who change dressing after seven days of CVC catheterization versus those who change dressing after 24 hours. The secondary objectives include comparing the incidence of CLABSI and medical adhesive-related skin injury (MRSI) between the two groups during CVC catheterization.

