2.2 Outcomes

2.2.1 Primary outcome

The primary outcome is the occurrence of skin bacterial colonization on the seventh or eighth day after CVC catheterization.

- Description:

For patients whose dressing is changed after seven days of CVC catheterization, skin samples will be taken on the seventh day after CVC. For patients whose dressing is changed after 24 hours of CVC catheterization, skin samples will be taken on the eighth day after CVC. The detailed sampling method is shown in the protocol. The colony number above 15 colony-forming units / cm² will be defined as skin bacterial colonization that occurred.

- Time Frame:

The experimental group will be detected on the seventh day after CVC catheterization. The control group will be detected on the eighth day after CVC catheterization.

- Type: binary variable: Yes / No.

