5.1. Primary Outcome Analysis

5.1.1 ITT analysis of the primary outcome - the primary analysis

The primary outcome is a binary outcome: the occurrence of skin bacterial colonization on the seventh or eighth day after CVC catheterization. The primary analysis will be based on the ITT population as defined above.

Hypothesis: Let π_1 denote the occurrence of skin bacterial colonization on the eighth day after CVC catheterization in the CD24h group (control group), and let π_2 denote the occurrence of skin bacterial colonization on the seventh day in the CD7d group (experimental group), the non-inferiority margin $\Delta=20\%$. The null hypothesis is $H_0: \pi_2 - \pi_1 > \Delta$ versus the alternative hypothesis is $H_A: \pi_2 - \pi_1 \leq \Delta$.

A generalized linear model (GLM) will be used to test the above hypothesis. In the GLM, the occurrence of skin bacterial colonization will be treated as the dependent variable and the treatment as the fixed effect, following a binomial distribution and identity link function. A point estimate of risk difference between groups in the difference and its 95% confidence interval (CI) will be estimated. CD7d treatment will be considered non-inferior to the CD24h treatment if the upper 95% confidence limit is no greater than Δ , where $\Delta= 20\%$, the predetermined non-inferiority margin.

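### Does the ambiguous per-protocol exclusion for the CD24h group leave the per-protocol population undefined?

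*SAP*

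**What the plan says.** Section 4.1 sets a general rule for the per-protocol set: the "population will only include patients who received the treatments according to the protocol". It adds a sampling condition (day 7 for CD7d, day 8 for CD24h). It then lists two grounds for exclusion: non-adherence and switching treatment. Non-adherence is illustrated by one example per arm. For CD7d it is a dressing change before seven days. For the control arm it is that "the CD24h group does not change the dressing more than 24 hours after CVC catheterization".

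The control treatment is described in three other places:

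- Section 2.1 speaks of "those who change dressing after 24 hours".
- Section 2.2.1 has "For patients whose dressing is changed after 24 hours of CVC catheterization", with the sample on day 8.
- Section 3.3 has "The dressing change will be performed 24 hours after CVC catheterization in the operating room or PICU". For the step that follows, the same section states that "the second dressing change will be completed seven days later".

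On the role of the set, section 4.1 says "This population will be used for the supportive analyses". Section 5.1.1 says "The primary analysis will be based on the ITT population as defined above".

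**The concern.** The control-arm example can be read in two ways.

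- **Sense A:** the child is excluded unless the change came later than 24 hours after insertion.
- **Sense B:** the child is excluded once more than 24 hours have passed without a change.

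Read literally, these are complements. Any control child with a first change is kept by one and dropped by the other. Neither fits the described treatment. A drops a change made exactly at 24 hours and keeps one made days later. B drops a change made shortly after 24 hours and keeps one made very early. The clause also does not say that it means the first change. If the scheduled second change counted, A would exclude no child who had it.

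Per-protocol results matter in a non-inferiority trial, because departures from assigned treatment can make two arms look alike. They fill two of the four rows of the SAP's Table 2. The criterion is specific to one arm, so it can be applied only with the allocation in hand. If its sense were still open at that point, it could be chosen with knowledge of the allocation.

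**Working it through.** **1. The two literal senses.** Let t be the time of the first control-arm change in hours. A keeps t > 24; B keeps t ≤ 24.

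| First change | Sense A | Sense B |
|---|---|---|
| 2 h | excluded | kept |
| 20 h | excluded | kept |
| 24 h | excluded | kept |
| 26 h | kept | excluded |
| 72 h | kept | excluded |
| 120 h | kept | excluded |
| never | excluded | excluded |

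The two agree only on a child who was never changed. As a statement about the isolated clause, the concern is correct.

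**2. The clause within section 4.1.** The clause is introduced as something included under non-adherence. It illustrates the general rule and does not replace it. A child must pass the general rule as well as the example. A first change at 72 hours passes A but is not the treatment in section 3.3. A change at 2 hours passes B but is not that treatment either. Neither child belongs in the set under the general rule, so the table does not describe the per-protocol population.

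**3. What the schedule implies.** Section 3.3 puts the first control change at 24 hours (day 1) and the second seven days later: 1 + 7 = 8, the control sampling day. A first change at 72 hours (day 3) would put the second at 3 + 7 = 10, off that schedule. The 24 hours is therefore a nominal time point. The wording in sections 2.1 and 2.2.1 is used in the same form for the seven-day arm and also names nominal times.

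**4. The two examples side by side.** The CD7d example describes a child changed too soon for the seven-day schedule. The CD24h example is most sensibly its counterpart: a child who did not get the scheduled 24-hour change. Each names the departure that would make the child resemble the other arm. This also settles which change is meant. Both arms have a dressing change at sampling, so letting the control arm's second change satisfy the clause would empty it of content.

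**5. Size under an extreme assumption.** The plan's own figure first. With 55% in both arms, margin 0.20, one-sided alpha 0.025 and 80% power, the sample-size calculation gives 98 per group, and 98/0.70 = 140, both as stated in section 3.6. Now suppose the clause alone were programmed with a strict cut, and a share g of 98 control children were first changed after 24 hours. The SAP gives no value for g. A keeps round(98g) and B keeps the rest: 10 and 88 at g = 10%, 49 and 49 at 50%, 88 and 10 at 90%. With 98 CD7d children, the 95% half-width of the difference is

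1.96 × √(0.55 × 0.45 × (1/n + 1/98)),

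which is 32.4 points at n = 10, 17.1 at n = 49, 14.3 at n = 88, and 13.9 with no exclusion (n = 98). The large values need both an extreme g and disregard of the general rule. They are not an estimate for this trial.

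**6. Blinding.** Section 3.5 has the trial statistician blinded while developing the SAP and writing the programs, with the allocation given to the study team only after database lock. A rule specific to one arm can be coded in advance and applied when the allocation arrives.

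**The case for a change.** The best case for a change is that the SAP states the criterion itself and states it badly, so this is not simply a matter left to the protocol. A named example is meant to make a general rule concrete, and this one obscures it. The sampling condition does not rescue it, since a control child first changed at 72 hours could still be sampled on day 8. Switching treatment is not defined and may catch only gross cases. Sense A has a real textual claim: it mirrors the grammar of the CD7d example, and it agrees with sections 2.1 and 2.2.1 if their wording is taken as open-ended. Rewording would cost one sentence.

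Most of this stands as a remark on drafting. The phrase is ambiguous, it omits which change is meant, and no tolerance around 24 hours is given. What does not stand is the step to an undefined population. The remedy on offer would name the first change and point to the protocol's own window, which the general rule already does. It supplies no better rule. A tolerance around a scheduled time is a detail a SAP commonly leaves to the protocol, and the protocol is not to hand.

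Two side points carry little weight. The variable list in section 7 has no time of dressing change, but it also lacks the sampling date, the time of MARSI and the administration set, all of which the analyses need; it is not a full inventory. How a clinically indicated early change is classified is not spelled out in the examples, but section 3.3 already makes both schedules conditional on there being no such indication.

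**Conclusion.** The concern is right about the sentence and wrong about its consequence. The clause is clumsy and, in isolation, supports two opposite rules. In context it is an illustration beneath a rule that requires treatment as the protocol defines it, and the schedule in section 3.3 shows what is being illustrated. An analyst would fill the gap by excluding control children who did not receive the scheduled 24-hour change.

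The reach is small. The primary non-inferiority decision and the sample size are unaffected. Only the per-protocol and adjusted per-protocol sensitivity analyses depend on the clause, and neither the size nor the direction of any effect on them can be derived from the SAP.

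This conclusion rests on two assumptions: that the protocol defines the 24-hour change well enough for adherence to be judged, and that the rule is coded while the statistician is blinded, as section 3.5 provides.

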4.2 Study Close Date

The data collection close date is when the last patient removed the CVC to achieve outcomes.

4.3 Data Cleaning

The data will then be checked to ensure no erroneous entries and that all missing data is properly coded. Any changes will be made to the database.

4.4 Data Check-up

Once all data have been inputted and checked, the database will be locked and a data download request made. The data will be downloaded into SAS and Stata formats for

statistical analyses.

5. Statistical Analyses

5.1. Primary Outcome Analysis

5.1.1 ITT analysis of the primary outcome - the primary analysis

The primary outcome is a binary outcome: the occurrence of skin bacterial colonization on the seventh or eighth day after CVC catheterization. The primary analysis will be based on the ITT population as defined above.

Hypothesis: Let π_1 denote the occurrence of skin bacterial colonization on the eighth day after CVC catheterization in the CD24h group (control group), and let π_2 denote the occurrence of skin bacterial colonization on the seventh day in the CD7d group (experimental group), the non-inferiority margin $\Delta=20\%$. The null hypothesis is $H_0: \pi_2 - \pi_1 > \Delta$ versus the alternative hypothesis is $H_A: \pi_2 - \pi_1 \leq \Delta$.

A generalized linear model (GLM) will be used to test the above hypothesis. In the GLM, the occurrence of skin bacterial colonization will be treated as the dependent variable and the treatment as the fixed effect, following a binomial distribution and identity link function. A point estimate of risk difference between groups in the difference and its 95% confidence interval (CI) will be estimated. CD7d treatment will be considered non-inferior to the CD24h treatment if the upper 95% confidence limit is no greater than Δ , where $\Delta= 20\%$, the predetermined non-inferiority margin.

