3.2 Trial Sites

The trial will be conducted in four hospitals in China: Children's Hospital of Fudan University, Xiamen Children's Hospital, Shenzhen Children's Hospital, and Anhui Province Children's Hospital.

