3.4 Randomization

Central block randomization with a block size of 4 will be used in this trial. Eligible patients will be randomly assigned to the control arm or the experimental arm (allocation ratio 1:1). According to the seed generated by an independent statistician using SAS software (version 9.4), a sequence of study numbers and randomized allocations will be generated. The allocation sequence will be concealed and placed in the non-transparent sealed envelopes by the independent statistical group from the Clinical Trial Unit (CTU) of the Children's Hospital of Fudan University: the four allocations of each block will be placed in the four sealed small envelopes numbered 1 to 4 in order, and then put into the same large envelope marked with the corresponding block number.

Before each site enrolls the first patient of the block, the coordinator will contact the central coordinator of Children's Hospital of Fudan University, and the central coordinator will assign the envelopes to each site. The clinical nurse in each site will assess the eligibility of the patients and obtain signed informed consent, and then contact the coordinator to obtain the allocation. The coordinator will open the envelopes in numbered order according to the enrollment order, inform the nurse of the allocation, and record the assignment of each enrolled patient.

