3.6 Sample Size

This study is a non-inferiority design, and the primary outcome is the occurrence of skin bacterial colonization on the seventh or eighth day after CVC catheterization (binary outcome). The sample size is calculated based on the difference between the two groups of the primary outcome.

According to our previous pilot study that included 49 subjects, the occurrence of skin bacterial colonization in the CD7d group and the CD24h group was 56.3% and 55.6%, respectively. A non-inferiority margin of 20% is considered to be clinically acceptable. Based on the assumptions of (i) the occurrence of skin bacterial colonization of 55% in the CD24h group, (ii) the non-inferiority margin of 20%, (iii) power of 80%, and (iv) a one-sided alpha of 0.025, the sample size estimation resulted in 98 subjects per group (calculated with PASS software, version 16.0). Considering a 30% drop-out rate, a total of 280 subjects should be randomized (140 per group).

4. Analysis Populations

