5.1.2 Sensitivity analyses of the primary outcome

- PP analysis with GLM (described in 5.1.1) will be performed.
- An analysis of the primary outcome will be adjusted for age, gender, CVC catheterization site, type of disease, and administration set at baseline in ITT and PP population, respectively. The adjusted difference and 95% one-sided upper limit comparing the two groups will be derived by GLM (described in 5.1.1). If the above identity-binomial GLM does not converge when all covariates are introduced into the model, the adjusted model will be performed by removing a covariate one by one until the model converges.

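### Blocks of four are used within single hospitals, but hospital is in neither the primary nor the adjusted model, so the interval is somewhat too wide if hospitals differ

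*SAP*

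**What the plan says.** **Randomisation.** "The trial will be conducted in four hospitals in China" (SAP 3.2). Section 3.4 uses a fixed block size of 4 with 1:1 allocation. The four allocations of a block go into small numbered envelopes that are then "put into the same large envelope marked with the corresponding block number". A site asks for an envelope before it enrols the first patient of a block, and "the central coordinator will assign the envelopes to each site". The SAP does not call this stratification, but each block is used up within one hospital.

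**Analysis.** In the primary binomial GLM with identity link, "the occurrence of skin bacterial colonization will be treated as the dependent variable and the treatment as the fixed effect" (5.1.1). No other term is listed. The adjusted sensitivity analyses are "adjusted for age, gender, CVC catheterization site, type of disease, and administration set at baseline" (5.1.2), again without hospital. If that model fails to converge, "the adjusted model will be performed by removing a covariate one by one until the model converges", with no order given.

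**Data.** Section 7 lists both the name and the number of the centre, so hospital is recorded. No section plans a centre term, a stratified estimate, a random effect or a centre subgroup. Section 3.6 allows for 30% drop-out, and section 4.1 states: "Participants will be excluded from the ITT analysis if the primary outcome is missing".

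**The concern.** Blocking within hospitals keeps differences between hospitals out of the comparison of the arms. A model with treatment alone still counts those differences as random error. Its standard error is then larger than the true one, and the upper confidence limit sits further out than it should. That limit alone decides non-inferiority, so a trial of an equivalent dressing schedule could miss the margin more often than necessary.

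The adjusted analyses do not repair this, because hospital is missing there too. They have a weakness of their own: an unordered drop-until-converged rule leaves a data-dependent choice. The adjusted ITT and PP rows of Table 2 could rest on different covariates, although the table's footnotes promise the same five for each.

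**Working it through.** **1. The plan's own figure.** Inputs from section 3.6: 55% in both arms, margin 0.20, one-sided alpha 0.025, power 80%.

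n = (1.960 + 0.842)² × 2 × 0.55 × 0.45 / 0.20² = 97.1, so 98 per group; 98 / 0.70 = 140 per group, 280 in total. Both figures reproduce.

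**2. Assumptions.** The SAP gives no rates by hospital. I take four equal hospitals averaging 55%, no true difference between the arms, and 98 analysed per arm. Three spreads are used: 45/50/60/65%, 40/50/60/70% and, as an extreme, 30/45/65/80%.

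**3. Closed form.**

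- Standard error the planned model reports: SE_u = √(2 × 0.55 × 0.45 / 98) = 0.0711.
- True standard error with blocks within hospitals: SE_t = √(2 × mean[p_k(1 − p_k)] / 98). The means are 0.24125, 0.235 and 0.21125, against 0.2475 with no spread.
- Half-width: 1.96 × SE.
- Power of the planned model: Φ((0.20 − 1.96 SE_u) / SE_t).
- Power of the stratified analysis: Φ(0.20 / SE_t − 1.96).

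| Hospital rates | SE_t | Half-width, planned | Half-width, stratified | Power, planned | Power, stratified |
|---|---|---|---|---|---|
| 45/50/60/65% | 0.0702 | 13.93 | 13.75 | 80.7% | 81.3% |
| 40/50/60/70% | 0.0693 | 13.93 | 13.57 | 81.0% | 82.3% |
| 30/45/65/80% | 0.0657 | 13.93 | 12.87 | 82.2% | 86.1% |

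**4. Type I error of the planned model.** At the null (55% vs 75%), SE_u = √((0.2475 + 0.1875) / 98) = 0.0666. The true values, with every experimental rate raised by 20 points, are 0.0657, 0.0647 and 0.0608. Φ(−1.96 × SE_u / SE_t) gives 2.34%, 2.18% and 1.59%, all below the nominal 2.5%.

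**5. Simulation with drop-out.** Excluding patients without an outcome makes the balance by hospital only approximate, so this was simulated: 400,000 trials per scenario, 36/34/36/34 randomised per arm in whole blocks, and each patient lost at random with probability 0.30. The unadjusted Wald interval was compared with Mantel-Haenszel using the Sato variance.

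| Hospital rates | Power, planned | Power, stratified | Gain (points) | Type I, planned | Type I, stratified |
|---|---|---|---|---|---|
| No spread | 80.43% | 80.25% | −0.2 | – | – |
| 45/50/60/65% | 80.67% | 81.29% | 0.6 | 2.34% | 2.46% |
| 40/50/60/70% | 80.75% | 82.18% | 1.4 | 2.19% | 2.44% |
| 30/45/65/80% | 81.76% | 86.08% | 4.3 | 1.76% | 2.51% |

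In the last row, the type I calculation puts one hospital at 80% + 20 = 100%.

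**6. Unequal hospitals.** With 70/28/22/20 per arm, power moves from 80.31 to 80.87%, 80.57 to 81.92% and 81.51 to 85.66%. With the sizes reversed it moves from 81.45 to 82.01%, 82.25 to 83.60% and 84.62 to 88.69%. The gains are therefore about the same. Stratified type I error is 2.4–2.6%, or 2.7% when the largest hospital would be at 100%.

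**7. Source of the effect.** In a separate simulation (40,000 runs per scenario) with randomisation not blocked within hospitals, the planned model's type I error stayed at 2.3–2.5%. The conservatism therefore comes from the within-hospital blocks.

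**The case against.** The best defence is that nothing in the decision is wrong. Section 3.6 sizes the trial on an unstratified comparison and section 5.1.1 analyses it in the same way. The test errs on the safe side and the planned power is reached. The gain rests entirely on assumed hospital rates, and the largest figure needs hospitals at 30% and 80%. In the separate simulation, with a slightly more cautious stratified variance, stratifying gained nothing at a range of 48–62% (80.8% planned, 80.6% stratified) and lost 0.4 points with no spread. The remedy also adds a pooling rule, and in one extreme case its type I error is 2.7%.

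All of this stands, and it limits the size of the point. It does not remove it: the possible loss is a few tenths of a point of power, the possible gain is larger, and no further patients or data are needed. A centre adjustment introduced after results are known would be open to challenge, so the choice belongs in the SAP now.

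On the drop rule, an illustrative simulation with an assumed covariate mix put the full model's fit on the 0 or 1 boundary in 5.6% of trials with no covariate effects and in 36.3% with moderate ones. A boundary fit is not the same event as non-convergence, so I do not read these as estimates of how often covariates would be dropped. The missing order is a gap at any frequency.

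**Conclusion.** The point holds as a loss of efficiency, not of validity. The primary analysis ignores the grouping within which patients are randomised; its test is slightly conservative and its power stays at or above 80%. The realistic cost is about 0.6 to 1.4 points of power, for hospital rates spanning 20 to 30 points. The 4.3 points at a 50-point span are an upper illustration. These figures assume an average of 55%, no true difference and drop-out unrelated to outcome; if hospitals are alike there is no gain. The unordered drop rule cannot change the non-inferiority decision, but it can make the adjusted ITT and PP results not comparable. The change should be made, though the trial does not fail without it.

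**What to change.** - **Primary analysis (5.1.1).** Estimate the risk difference, CD7d minus CD24h, by Mantel-Haenszel stratified by hospital, with a two-sided 95% CI using the Sato variance, against the same 20-point margin. State in advance how a hospital with very few analysed patients is pooled. Keep the unstratified GLM as a sensitivity analysis.
- **Adjusted analyses (5.1.2).** Replace the drop-until-converged rule with a logistic model containing treatment, hospital and the fixed covariate list. Standardise it to a risk difference with a delta-method or bootstrap CI, and use the same covariates in ITT and PP. At the least, fix one removal order and one common covariate set for both populations.

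**Cost.** SAP wording and minor programming. Hospital is already recorded and the sample size does not change. The price is a slightly more complex estimator, a pooling rule to write down, and about 0.2 to 0.4 points of power if hospitals turn out not to differ.
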